	b) Urogenital, product-related, and/or serious AEs among female and male participants during Ovaprene™ use.	Ovaprene™ safety cycle and Ovaprene™ PCT cycles
	c) Changes from baseline in complete blood count, serum chemistries, and serum ferritin	Ovaprene™ safety cycle
	d) Changes from baseline in findings on pelvic exam, including colposcopy.	Ovaprene™ safety cycle and Ovaprene™ PCT cycles

Version: 06.00 (FINAL) Date: June 13, 2019

	e) Changes from baseline in:	Ovaprene™ safety cycle
	
 
Nugent score and microflora
 
	and Ovaprene™ PCT
	
 
Antibacterial (anti-E. coli) activity in CVF
 
	cycles
	
 
Soluble markers of inflammation in CVF
 
	
	f) Presence of Staphylococcus aureus or group A Streptococcus on Ovaprene™ devices that have been worn over a cycle of use	Ovaprene™ safety cycle and Ovaprene™ PCT
		cycles
Tertiary:	a) Responses on acceptability questionnaire/diary:	Ovaprene™ safety cycle
4. Acceptability	
 
Problems with insertion, including confirmation of placement
 
	and Ovaprene™ PCT
	
 
Aspects liked most and least by the female partner
 
	cycles
	
 
Dislodgements reported by the female partner
 
	
	
 
Comfort reported by both partners during intercourse and
 
	
	whether discomfort, if reported, was bothersome and would	
	keep the person from using the device again	- II I
5. Fit	a) Proportion of participants who can be fitted with Ovaprene™.	Baseline PCT cycle
	b) Proportion of participants who can correctly insert, position, and	Baseline PCT cycle,
	remove the device using written instructions only.	Ovaprene™ safety cycle,
		and Ovaprene™ PCT cycles
	c) Proportion of participants who require assistance to correctly	Baseline PCT cycle,
	insert, position, and remove the device.	Ovaprene™ safety cycle,
		and Ovaprene™ PCT
		cycles
	d) Location of Ovaprene™ in relation to the cervix as determined by	Ovaprene™ safety cycle
	clinical exam; relationship of position to PCT results, safety, and	and Ovaprene™ PCT
	acceptability.	cycles

Version: 06.00 (FINAL) Date: June 13, 2019

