#### b) Visit OS2, 24 hours after insertion:

- Diary review, AEs, medications, and indications for a directed physical exam, wet mount, and other tests will be managed as described for Visit 2 (BP1).
- The participant will undergo a pelvic exam:
  - o Signs of irritation of the external genitalia, cervix, and vagina, as observed with the naked eye, will be noted.
  - o The position of the device relative to the cervix will be noted.
  - o Vaginal sample(s) will be collected for ferrous gluconate, pH, Nugent score, microflora, antibacterial activity, and soluble markers.
- An ovulation predictor kit (OPK) with instructions will be dispensed. The participant will be instructed to:
  - o Begin daily urine testing on day 10 of that cycle (adjusted as needed to normal cycle length); and
  - o Contact the study coordinator when the OPK test yields a "high" result, if that takes place before OS3 is scheduled. If possible, OS3 will be scheduled for that day or the next day. If that is not possible, OS3 will take place 7-9 days after insertion (approximately cycle day 13 -15).
- c) Visit OS3, 7-9 days after insertion (approximately cycle day 13 -15, unless a "high" OPK result takes place):

° It is expected that ferrous gluconate will not be found in the vaginal sample before the device is inserted. Samples taken before insertion will serve as a negative control.

<sup>p Samples will be collected at as many of these timepoints as possible.

Version: 06.00 (FINAL) Date: June 13, 2019

- The procedures described above for Visit OS2 will be completed, except that no OPK will be dispensed.
- In addition, cervical mucus will be collected for ferrous gluconateq and pH.

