# e) Visit OS5, 21-23 days after insertion (approximately cycle day 27-29, or sooner if menses is expected to begin):

- An acceptability questionnaire will be administered.
- Blood will be drawn for CBC, serum chemistries, and serum ferritin.
- The procedures described above for Visit OS2 will be completed, except that no OPK will be dispensed.
- Ovaprene™ will be removed and stored for later analysis.
- A colposcopic exam will be completed.
- Cervical mucus will be collected for ferrous gluconate and pH.
- The participant will next undergo an Ovaprene™ PCT cycle. She will be instructed to:
  - o Call at the onset of her next menses to tentatively schedule Visit OP1 on the day following the end of menses. Adjustments to this visit will be made as needed.
  - Use non-spermicidal, lubricated condoms (dispense as needed at this visit) from the first day of her next menses until day 10 of that cycle, and to abstain from intercourse and other vaginal activityr starting on Day 10 until after Visit OP2, the CMC visit.

<sup>q Assaying for ferrous gluconate in the cervical mucus is considered exploratory throughout the study.

"Other vaginal activity" includes insertion of vaginal medications/products other than the study product (prescription or over-the-counter), as well as insertion of sex toys, fingers, or anything else into the vagina. Tampons may be used during all days of menses in the Baseline PCT and Caya PCT cycles, but only during the first three days of menses in Ovaprene cycles.

Version: 06.00 (FINAL) Date: June 13, 2019

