# APPENDIX 1. SCHEDULE OF ASSESSMENTS

X = required O = if indicated

The pelvic exam procedures are listed in the recommended sequence of collection.

The pelvic exam procedures are listed in ti	ic recomme	lucu 3	cquem		Oncer	J11.											
	Screening	BP1	BP2	BP3	CP1	CP2	OS1	OS2	OS3	OS4	OS5	OP1	OP2	OP3	OP4	OP5	UNS
Informed Consent (also male, if																	
required)	Χ																
Assign Subject Number	Χ																
Demographics	Х																
Assess eligibility	Χ	Χ															
Enroll participant				Χ													
Medical/Obstetrical History 	Χ																Х
Directed Physical Exam 	0	0	0	0	0	0	0	0	0	0	0	0	0	0	0	0	Х
Height/Weight	Χ																Х
HIV 	Χ																Х
Urine Pregnancy Test	Х																Х
Urinalysis 	0	0	0	0	0	0	0	0	0	0	0	0	0	0	0	0	Х
CBC, Chemistry, Serum Ferritin	Χ						Χ				Χ						Х
Review Diary Entries		Χ	Х	Χ	Χ	Χ	Χ	Х	Х	Х	Х	Χ	Х	Χ	Χ	Χ	Х
AEs, Concomitant Medications		Χ	Х	Χ	Χ	Х	Χ	Х	Х	Х	Х	Χ	Х	Х	Х	Χ	Х
Acceptability Questionnaire											Х			Х			
Note device position by digital exam								Χ	Χ	Χ	Χ		Х	Х	Χ	Χ	Х
Pelvic exam - note irritation seen with																	
naked eye		Χ	Χ	Χ	Χ	Χ		Χ	Χ	Χ			Χ	Χ	Χ	Χ	Х
Exam of external genitalia, by naked																	
eye & colposcopy	X						Х				Х	Х				Х	Х
Colposcopic Exam - insert speculum, do naked eye exam of visible vaginal																	l
epithelium	Х						Х				Х	Х				Х	Х
Note device position with speculum in																	
place								Χ	Х	Χ	Х		Х	Х	Х	Х	Х
Vaginal pool - Trich test	Х																Х
Vaginal pool - Wet mount 	X	0	0	0	0	0	0	0	0	0	0	0	0	0	0	0	Х
Vaginal pool - ferrous gluconate							X 	Х	Х	Х	Х	Χ	Х	X 	Х	Χ	Χ

Version: 06.00 (FINAL) Date: June 13, 2019

Vaginal pool - Vaginal sperm evaluation		Х	Х		Х	Х							Х	Х			Х
Vaginal lateral wall - pH	Х	Χ	X 	Χ			X 	Χ	Х	Х	Χ	Х	Х	X 	Χ	Χ	Х
Vaginal lateral wall - Nugent Score	Χ						Χ	Χ	Х	Χ	Χ	Χ				Χ	Χ
Vaginal lateral wall - microflora		Χ	Χ	Χ			Χ	Χ	Χ	Х	Χ	Χ				Χ	Х
Vaginal lateral wall - back-up swab for																	
antibacterial activity, soluble markers		Χ	X 				X 	Χ	Χ	Χ	Χ	Χ		X 		Χ	Χ
Displace Ovaprene temporarily for																	1
specimen collection if necessary									Х		Х		Х	Х		Χ	Х
Cervical pH		Х	X 	Χ			Х		Х		Х	Х	Х	Х		Χ	Χ
Cervical mucus by pipette - midcycle		V	V		V	V							· ·	V			V

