#### 3.7.1 Adverse Events

An adverse event is any symptom, sign, illness, or experience that develops or worsens in severity and/or frequency after the date of informed consent. Each AE incidence will be assigned to one of the 3 Study Periods:

- (a) Baseline Cycle,
- (b) Caya® Cycle,
- (c) Ovaprene® Cycles,

depending on the AE start date within the time-frame of:

- (a) from date of consent through Cycle 1,
- (b) during Caya® cycle (Cycle 2),
- (c) in Cycles 3 through 5, respectively.

All adverse events will be coded with MedDRA 20.0. Incidence of adverse events will be summarized by system organ class (SOC) and preferred term (i.e., MedDRA term). The number and percent of subjects with each SOC and preferred term will be presented by the following 2 analysis populations:

- (i) Subject was treated Ovaprene, including AEs at Baseline and Ovaprene cycles
- (ii) Subject was treated with Caya, including AEs at Baseline and Caya cycles

Tables to summarize the incidence rates among female subjects (from those with answer "Female" to the question "Affected person?" in AE CRF) will be created for each of the following groups:

- Overall number and percent of subjects with AEs without presenting SOC or preferred term
- AEs by SOC and preferred term
- Study product-related AEs (including Possibly Related, Probably Related, and Definitely Related) by SOC and preferred term
- AEs presented in descending order of frequency by preferred term (without showing SOC), in which the most frequent one appears at first, and least frequent one will appear in the last
- AEs by SOC and preferred term and by severity
- · AEs by SOC and preferred term and by relationship to the study product
- AEs by SOC and preferred term for each Ovaprene cycle by subgroups of Ovaprene location (based on digital exam) where the following 2 subgroups are used: "Over cervical os", "Not over cervical os". If a subject has an assessment of "Not over cervical os" in the cycle then that will be the classification for that cycle. The "Not over cervical os" will be made up of the following 2 sub-categories: "Not over cervical os - on anterior vaginal wall", and "Not over cervical os and not on anterior vaginal wall".

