| Table Number | Table Title   | Population |
|--------------|---|-------------------|
| 14.3.1.6-Ca  | Number and Percent of Subjects with Adverse Events by System Organ Class and Preferred Term and by Relatedness to the Study Product for Caya Population | Caya              |
| 14.3.1.6     | Number and Percent of Subjects with Adverse Events by System Organ Class and Preferred Term and by Relatedness to the Study Product                     | Ovaprene          |
| 14.3.1.7     | Number and Percent of Subjects with Adverse Events by System Organ Class and Preferred Term for each Ovaprene Cycle by Subgroups of Device Position     | Ovaprene          |
| 14.3.2.1     | List of Serious Adverse Events  | Ovaprene          |
| 14.3.2.1-Ca  | List of Serious Adverse Events for Caya Population  | Caya              |
| 14.3.2.2     | List of Adverse Events that Led to Premature Study Discontinuation  | Ovaprene          |
| 14.3.2.2-Ca  | List of Adverse Events that Led to Premature Study Discontinuation for Caya Population  | Caya              |
| 14.3.2.3     | List of Urogenital System Adverse Events in Subjects and Male Partners  | Ovaprene          |
| 14.3.2.3-Ca  | List of Urogenital System Adverse Events in Subjects and Male Partners for Caya Population  | Caya              |
| 14.3.2.4     | List of Subjects who Developed a UTI During the Study   | Ovaprene          |
| 14.3.2.4-Ca  | List of Subjects who Developed a UTI During the Study for Caya Population   | Caya              |
| 14.3.5.1     | Hematology Test Results and Changes from Baseline to Each Visit   | Ovaprene          |
| 14.3.5.2     | Hematology Test Results and Shifts from Baseline to Each Visit  | Ovaprene          |
| 14.3.5.3     | Chemistry and Serum Ferritin Test Results and Changes from Baseline to Each Visit   | Ovaprene          |
| 14.3.5.4     | Chemistry and Serum Ferritin Test Results and Shifts from Baseline to Each Visit  | Ovaprene          |
| 14.3.5.5     | Summary of Urinalysis   | Ovaprene          |
| 14.3.5.6     | Summary of Colposcopic Findings   | Ovaprene          |
| 14.3.5.7-Ca  | Summary of Gynecological Examination for Caya Population  | Caya              |
| 14.3.5.7     | Summary of Gynecological Examination  | Ovaprene          |
| 14.3.5.8     | Summary of Nugent's Scores  | Ovaprene          |
| 14.3.5.9     | Summary of Soluble Markers and Antibacterial Tests  | Ovaprene          |

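### The table of adverse events by device position labels a whole Ovaprene cycle from any single off-os exam, so an event can be filed under a position first observed after it began

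*SAP*

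**What the plan says.** Fit endpoint 5d in Protocol section 6 covers device location by "clinical exam; relationship of position to PCT results, safety, and" acceptability. For the AE part of this, SAP 3.7.1 plans "AEs by SOC and preferred term for each Ovaprene cycle by subgroups of Ovaprene location (based on digital exam"), with two groups, over and not over the cervical os. A woman with any off-os assessment "in the cycle then that will be the classification for that cycle". The output is Table 14.3.1.7 in SAP 4.2.1, AEs "for each Ovaprene Cycle by Subgroups of Device Position". It is the only planned table of AEs by position.

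The AE start date is used to assign a study period, "depending on the AE start date within the time-frame of" three defined intervals. Neither SAP 3.7.1 nor the table list sets that date against the dates of the position exams.

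Two other parts of the documents do respect timing:

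- Protocol 14.2.6 plans a visit-level figure: of the visits with a recorded adverse safety outcome, the proportion with the device over the cervix. SAP 3.9 and the table list do not include it.
- In SAP 3.6, the PCT subgroups use device position when the PCT was done, and dislodgements reported earlier in the cycle than the PCT visit.

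**The concern.** Endpoint 5d asks whether AEs go with a displaced device. A label that can be set by an exam after the event does not answer that directly. An AE in the first week goes into the off-os group if the device is found off the os at the end of the cycle, even when every exam up to onset showed it in place. An AE that starts after a device has been found off the os and put back is likewise counted as off-os.

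The label also depends on how many times position was examined. AEs can lead to discontinuation (Protocol 7.5), which removes later exams. They can also prompt an unscheduled visit (Protocol 9.7), and the unscheduled column of Appendix 1 includes the digital exam. The AE itself can therefore alter the classification. The result may be to blur a relation between position and safety in a study that expects about 25 completers, where a few reassigned AEs would change the look of the table.

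**Working it through.** The plan states no figure to reproduce, so the check reads the rule against the visit schedule and then illustrates its size.

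**Inputs from the documents.** The row "Note device position by digital exam" in Protocol Appendix 1 is marked at four scheduled visits per Ovaprene cycle: OS2 to OS5, or OP2 to OP5. The safety cycle runs from "Visit OS2, 24 hours after insertion" to "Visit OS5, 21-23 days after insertion (approximately cycle day 27-29"). Approximate exam days after insertion are 1, 8, 15 and 22. In a PCT cycle, using the protocol's 28-day example with insertion on cycle day 6, they are 8, 9, 10 and 22.

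**Assumptions.** The probability q that one exam is off the os is not in the documents; the range used is 0.05 to 0.30. AE onset is uniform from insertion to day 22 and independent of position. Exams are independent in the first calculation.

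**1. Cycles labelled off-os.** P = 1 − (1 − q)^4.

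**2. AEs in labelled cycles that precede every off-os exam.** For an onset with k exams before it, the probability is (1 − q)^k × [1 − (1 − q)^(4−k)]. Average over onset and divide by P.

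Safety cycle, q = 0.20: k = 0, 1, 2, 3 occupy 1, 7, 7 and 7 of 22 days, with probabilities 0.5904, 0.3904, 0.2304 and 0.1024. The average is [0.5904 + 7 × 0.7232]/22 = 0.257, and 0.257/0.590 = 44%.

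| q | Cycles labelled | Onset before every off-os exam, safety cycle | Same, PCT cycle |
|---|---|---|---|
| 0.05 | 18.5% | 50% | 54% |
| 0.10 | 34.4% | 48% | 53% |
| 0.20 | 59.0% | 44% | 51% |
| 0.30 | 76.0% | 39% | 48% |

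**3. Other patterns of displacement.**

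- Displacement at a uniformly distributed time and lasting to the end of the cycle: 50% of AEs precede it.
- Exams within a cycle correlated at 0.6 (beta-binomial): 17%, 33% and 46% of cycles are labelled for q = 0.10, 0.20 and 0.30. Of the exams in those cycles, 1 − q/P = 42%, 39% and 35% still show the device over the os. This counts exams, not AEs.
- Position constant throughout the cycle: no AE is misfiled.

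**4. Dependence on exam count, q = 0.20.** One exam gives a 20% chance of the label, four give 59.0%, and five give 1 − 0.8^5 = 67.2%.

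**5. The alternative rule: last exam on or before onset.** Suppose a lasting displacement occurs at a uniform time and an AE follows 2 days later, by day 22, so displacement falls in days 0 to 20. In the safety cycle an exam falls between the two events for 1 + 2 + 2 = 5 of those 20 days, so 75% of such AEs are labelled over the os. In a PCT cycle the figure is 1 − 4/20 = 80%. With a 5-day lag the figures are 1 − 11/17 = 35% and 1 − 7/17 = 59%. The SAP's cycle label mislabels none of these, because the last exam catches the displacement.

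**The case against.** A good deal can be said for the SAP rule. An ever-off-os grouping is prespecified, simple and sensitive. Step 5 shows that ordering by onset makes the opposite error, filing AEs under over-the-os when displacement has happened but has not been seen. Position after an exam may also differ from position at it: SAP 3.9 f records attempts to push the device behind the pubic bone, and Appendix 1 provides for temporary displacement and replacement during sampling. The analysis is descriptive and serves part of a tertiary endpoint. By-subject listings of device position and AEs (16.2.5.2, 16.2.7.1A and B) would let a reader reconstruct the sequence. All of this stands. It argues for showing more than one view; it does not justify relying on the cycle label alone.

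A reader might infer three stronger things that the documents do not support:

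- **That AEs are attributed to a position the device did not yet have.** Exams are intermittent. A later off-os exam does not show that the device was over the os at onset; the rule simply does not check.
- **That women who withdraw because of an AE are placed preferentially in the over-the-os group.** Withdrawal removes exams, but AE-prompted unscheduled visits add them, and SAP 3.7.1 does not limit the rule to scheduled exams. The net direction is unknown.
- **That the rule hides a real relation between position and safety.** It can dilute one. How much depends on an off-os rate and a displacement pattern that the documents do not give.

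**Conclusion.** The point holds in a limited form. As written, an AE can be tabulated under a position first observed after it began, and the label depends on how many exams took place. Over an assumed off-os rate of 5% to 30% with independent exams and uniform onset, 39% to 54% of AEs in labelled cycles would precede every off-os exam. The figure is 50% under lasting displacement at a random time and zero if position is constant within a cycle. These figures illustrate the mechanism and do not predict the trial's result.

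The consequence is confined to Table 14.3.1.7 and the AE part of endpoint 5d. The primary PCT endpoint and its position subgroups are unaffected. The change is worth making because the protocol already plans a visit-level analysis that the SAP leaves out, and the data needed are scheduled to be collected.

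**What to change.** In SAP 3.7.1 and 4.2.1:

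1. Add the visit-level proportion from Protocol 14.2.6, read against the proportion of women with the device over the cervix at each visit, which that section also plans.
2. Tabulate each AE by the last digital-exam position on or before its onset date, starting from the clinician's placement check at OS1 or OP1. Show the position at the first exam after onset beside it, because displacement between exams is not observed. Appendix 1 does not mark the digital-exam row at OS1 and OP1, so state where the placement check is recorded.
3. Keep the present cycle-level split as a companion display, titled as ever off the os in the cycle.
4. Do not use device-days in a position as a denominator, because time in position is not observed.

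The cost is SAP wording and one or two extra descriptive tables from AE dates and visit positions already planned for collection. One limit remains: some AEs that follow an undetected displacement will still appear as over the os in the onset-ordered view, which is why the next exam and the cycle label should be shown with it.

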#### 3.7.2 Hematology, Chemistry and Serum Ferritin

Hematology, chemistry and serum ferritin changes from Baseline (Visit OS1) to Visit OS5 visit will be summarized by 6-number statistics. A summary of shifts from Baseline (Visit OS1) to Visit OS5 will be presented for each lab test parameter. The normal range for each parameter will be used to create categories of Low, Normal, or High. Any result that is higher (lower) than the upper (lower) limit of normal will be categorized as High (Low), and any result within the lower and upper limits of normal will be categorized as Normal. The number and percent of subjects in each category (Low, Normal, or High) from Baseline (Visit OS1) to Visit OS5 visit will be presented for each lab test parameter.

#### 3.7.3 Urinalysis

Urinalysis is only required if subject is symptomatic for urine tract infection (UTI). All urinalysis parameters, except for Specific Gravity, will be summarized categorically. Specific Gravity will be summarized by 6-number statistics.

#### 3.7.4 Colposcopy

Colposcopic assessment CRF does not have visit identifier. It will be linked with Visit CRF data by making the colposcopic assessment date to be equal to the visit date in Visit CRF, and then summarized categorically for the parameters in Colposcopic Findings CRF by visit:

- Were there any colposcopic findings? (Yes, No)
- If yes,
- Product related (No-present before product use, No-latrogenic, No-other, Yes-possibly, Yes-probably, Yes-definitely)
- Serious (Yes, No)
- Outcome (Resolved without sequelae, Resolved with sequelae, Finding still present at discontinuation/ exit, Subject died as a result of this finding, Unknown, subject lost to follow-up)
- Diagnosis (Normal, Erythema, Edema, Grossly white finding, Petechiae, Ecchymosis, Peeling, Ulcer, Abrasion, Laceration, Other)

Frequencies of each categorical result at Visit OS1 and Visit OS5 will be presented. The number and percentage of subjects with a worsening since baseline (OS1) of a finding will be summarized. The medical monitor will perform a review of the data to indicate subjects who had a worsening.

#### 3.7.5 Gynecological Examination

Gynecological examination will be performed during the screening and after the study device placement in the following areas, and the results at the last assessment before the device placement will be summarized categorically ("Normal", "Abnormal") by visit.

- Vulva (Normal, Abnormal)
- Vaginal (Normal, Abnormal)
- Cervix (Normal, Abnormal)

- Adnexae (Normal, Abnormal)
- Uterus (Normal, Abnormal)

The number of subjects with clinically significant result in gynecological examination will also be presented. Change from Baseline results will be classified and defined as follows, and then summarized categorically at each post-baseline visit.

- "Improved" = if Abnormal at Baseline and Normal at post-Baseline;
- "No Change" = if post-Baseline result is the same as the Baseline;
- "Worsened" = if Normal at Baseline and Abnormal at post-Baseline.

#### 3.7.6 Nugent's Score and Vaginal Microflora

Nugent's score (from central lab, if available; otherwise, use local lab) and antibacterial (anti-E. coli) activity in CVF, soluble markers of inflammation in CVF and changes in these endpoints from Visit OS1 to OS2 through OS5 and from Visit OP1 to OP5, will be summarized by 6-number statistics at each visit. Antibacterial and soluble marker changes will also be summaries for these changes: BP1 to OS1, BP2 to OP3 and OP1 to OP3. Vaginal microflora and staphylococcus aureus assessment on the ring will not be analyzed by HD and the vendor analysis of the data will be included as an appendix of the final clinical study report.

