#### **Duration of treatment:**

Ovaprene™ will be used in 3 scheduled menstrual cycles

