#### c) Visit 4 (BP3) - 24 hours after the PCT

- Diary review, AEs, medications, and indications for a directed physical exam, wet mount, or other tests will be managed as described for Visit 2 (BP1).
- The participant will undergo a pelvic exam:
  - o Signs of irritation of the external genitalia, cervix, and vagina, as observed with the naked eye, will be noted.
  - o Cervical mucus will be examined for assessment of pH.
  - o Vaginal sample(s) will be examined for an assessment of pH and baseline microflora.
- The investigator will insert Ovaprene™ and assess the fit (Appendix 3). If the investigator determines that Ovaprene™ fits appropriately, she/he will remove it and give the device and written product instructions to the participant. The participant will then attempt to insert Ovaprene™ without assistance. If she is able to insert it, the investigator will check the placement. If the participant is unable to correctly insert and position the device, the investigator will reinstruct and assist as needed. Once the participant correctly inserts and positions the device, she will be asked to remove it. If she is not able to remove the device, the investigator will reinstruct her and assist as needed.
- If the investigator determines the Ovaprene® device does not fit appropriately, or if the participant cannot correctly insert, position, and remove the device, even with assistance, the participant will not continue.

<sup>1 These will serve as baseline measurements for comparison with those obtained at the PCT visits (OP3) in Ovaprene PCT Cycles.

<sup>j Samples will be collected at as many of these timepoints as possible.

<sup>k These will serve as baseline measurements for comparison with those obtained at the PCT visits (OP3) in Ovaprene PCT Cycles.

Version: 06.00 (FINAL) Date: June 13, 2019

Participants with successful baseline cycles will be considered enrolled.

- An ovulation predictor kit (OPK) with instructions will be dispensed. The participant will be instructed to:
  - o Contact the site at the onset of her next menses;
  - o Begin daily urine testing on day 10 of that cycle (adjusted as needed to normal cycle length); and
  - Contact the study coordinator when the OPK test yields a "high" result. Visit
     CP1 the mucus check visit in the Caya PCT cycle will be scheduled for that day or the next day.

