# 9.5.1 Ovaprene™ PCT Cycle - Visits and Procedures:

#### a) Visit OP1, the day following the end of menses (approximately cycle day 6):

• Diary review, AEs, medications, and indications for a directed physical exam, wet mount, and other tests will be managed as described for Visit 2 (BP1).

Version: 06.00 (FINAL) Date: June 13, 2019

- The participant will be asked whether she used non-spermicidal, lubricated condoms
  from the onset of menses in this cycle. If instructions were not followed, she will be
  reinstructed. If she used a spermicide or spermicidal lubricated condom, Visit OP1 will
  be rescheduled in the next cycle. Otherwise, the visit may continue at the
  investigator's discretion.
- The participant will undergo a pelvic exam:
  - o Signs of irritation of the external genitalia, cervix, and vagina, as observed with the naked eye, will be noted.
  - o A colposcopic exam will be completed.
  - o Cervical mucus will be collected for pH and ferrous gluconate.
  - o Vaginal sample(s) will be collected for pH, ferrous gluconate, Nugent score, microflora, antibacterial activity, and soluble markers.
- The participant will insert Ovaprene™ using written instructions, with assistance if needed. The clinician will check the placement.
- An ovulation predictor kit (OPK) with instructions will be dispensed.
- The participant will be instructed as follows:
  - Begin daily urine testing on day 10 of that cycle (adjusted as needed to normal cycle length) and contact the study coordinator when the OPK test yields a "high" result. Visit OP2 (the mucus check visits) will then be scheduled for that day or the next day.
  - O Until day 10, she and her partner should use condoms for each act of intercourse. There should be no intercourse or other vaginal activity,s and her male partner should not have an ejaculation, starting on day 10 until after Visit OP3.

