**Table 14: Endpoint Evaluations** 

	Goal	Baseline	Compared with
Changes in CBC,* chemistries,* and ferritin, colposcopy*	Assess effect of device on these endpoints after one cycle of use in the absence of sex, compared with before insertion	OS1	OS5
Nugent score,* vaginal microflora, vaginal antibacterial	Assess effect of device on these endpoints over one cycle, in the absence of sex, compared with before insertion	OS1	OS2, OS3, OS4, OS5
activity, and soluble markers	Assess effect of device on these endpoints after the device has been in place for one cycle, with multiple acts of sex up until 72 hours before the last visit, compared with before insertion	OP1	OP5
Vaginal antibacterial activity and soluble markers of inflammation	Assess effect of device insertion on these markers, in the absence of sex	BP1	OS1 after device insertion Baseline sample cannot be collected before device insertion at this visit because collection technique (vaginal lavage) is likely to affect subsequent samples taken at this visit.
	Assess effect of device on these markers after sex, compared with after sex with no device in place	BP2	OP3
	Assess effect of device on these markers after sex, compared with before sex	OP1	OP3

\* Also done at Visit 1 to establish eligibility

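### No planned paired change links a PCT-cycle Nugent score, or an end-of-cycle (OP5) CVF marker value, to a value from before Ovaprene was first worn

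*SAP*

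**What the plan says.** The Protocol synopsis states that the device "will be used in 3 scheduled menstrual cycles". These are the safety cycle (Cycle 3) and the two Ovaprene PCT cycles (Cycles 4 and 5, visits suffixed A and B in the SAP).

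Safety endpoint 3e (Protocol section 6, SAP 2.4) is change from baseline in Nugent score, microflora, antibacterial activity and soluble markers, in the safety cycle and in the PCT cycles.

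For Nugent score and the markers, SAP 3.7.6 says that "changes in these endpoints from Visit OS1 to OS2 through OS5 and from Visit OP1 to OP5, will be summarized by 6-number statistics". For the markers only it adds: "Antibacterial and soluble marker changes will also be summaries for these changes: BP1 to OS1, BP2 to OP3 and OP1 to OP3". Microflora is left to the vendor's own analysis and is outside this point.

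Protocol Table 14 lists the same visit pairs. Its aim for OP1 to OP5 is the effect "after the device has been in place for one cycle, with multiple acts of sex up until 72 hours before the last visit", against a pre-insertion value. Its aim for BP2 to OP3 is "Assess effect of device on these markers after sex, compared with after sex with no device in place". A footnote in Protocol 9.2.1 says of the BP2 marker samples: "These will serve as baseline measurements for comparison with those obtained at the PCT visits (OP3) in Ovaprene PCT Cycles".

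At OP1, before the device goes in, Protocol 9.5.1 specifies: "Vaginal sample(s) will be collected for pH, ferrous gluconate, Nugent score, microflora, antibacterial activity, and soluble markers". OP5 repeats these measurements at the end of the cycle.

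**The concern.** OP1 precedes insertion of that cycle's device, but it does not precede exposure to Ovaprene. In the protocol's 28-day example the device comes out on about day 28 and the next goes in on about day 6, which leaves about six device-free days. If vaginal flora or a marker has shifted and not fully recovered by then, the residual shift is in the new baseline and is subtracted from the OP1-to-OP5 change.

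The device is meant for back-to-back monthly use. For such a product, the vaginal-safety question that most needs an answer is where a woman stands after several cycles relative to where she began. Endpoint 3e asks for change from baseline in the PCT cycles, and a baseline taken after one or two cycles of wear answers only the within-cycle part. Elsewhere the SAP takes OS1 as baseline (laboratory tests in 3.7.2, colposcopy in 3.7.4) and compares across cycles where it wants to (acceptability shifts from OS5 to OP3A and OP3B in 3.8).

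**Working it through.** The plan gives no effect size, SD or power for these endpoints, and the sample size is not statistical, so there is no figure to reproduce. The check has two parts.

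**1. Planned visit pairs against prior wear** (SAP 3.7.6, Protocol Table 14, visit order from Protocol 7.1)

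| Planned change | Endpoints | Ovaprene cycles worn before the baseline visit | How far it reaches |
|---|---|---|---|
| OS1 to OS2–OS5 | Nugent, markers | 0 | end of first Ovaprene cycle |
| OP1 to OP5 | Nugent, markers | 1 (A) or 2 (B) | end of second or third |
| BP1 to OS1 | markers | 0 | day of first insertion |
| BP2 to OP3 | markers | 0 | middle of second and third |
| OP1 to OP3 | markers | 1 (A) or 2 (B) | middle of second or third |

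Pairs linking a PCT-cycle visit to a value before first wear: none for Nugent score, one (BP2 to OP3) for the markers. Pairs linking OP5 to such a value: none for either.

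**2. Illustration of size.** Both inputs are assumptions. Let each cycle of wear add a shift d, and let a fraction r of the level at removal remain at the next OP1. Set the value before first wear to 0.

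- OS5 = d
- OP1A = rd, and OP5A = d(1 + r)
- OP1B = d(r + r²), and OP5B = d(1 + r + r²)
- Planned change OP1B to OP5B = d, whatever r is
- Change OS1 to OP5B = d(1 + r + r²)
- Share left out = 1 − 1/(1 + r + r²)

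For the markers, assume that the shift is linear over wear from day 6 to day 28 with the PCT on day 15. The fraction of the within-cycle shift reached is (15 − 6)/(28 − 6) = 9/22 = 0.41, so BP2 to OP3B = d(r + r² + 0.41).

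| r | OS1 to OP5B | OP1B to OP5B | Share left out | BP2 to OP3B (markers) | As share of OS1 to OP5B |
|---|---|---|---|---|---|
| 0 | 1.00d | 1.00d | 0% | 0.41d | 41% |
| 0.25 | 1.31d | 1.00d | 24% | 0.72d | 55% |
| 0.5 | 1.75d | 1.00d | 43% | 1.16d | 66% |
| 0.75 | 2.31d | 1.00d | 57% | 1.72d | 74% |
| 1 | 3.00d | 1.00d | 67% | 2.41d | 80% |

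**Which OP1 and OP5.** SAP 3.7.6 does not say whether OP1 to OP5 is done within A and within B. The SAP schedule, as it reads in the text available, marks Nugent score only at OP1A and OP5B among the PCT-cycle visits, whereas Protocol 9.5.1 collects it at OP1 and OP5 of an Ovaprene PCT cycle without restricting it to one of the two. The SAP table may have been misread on extraction. If OP1A to OP5B were meant, the change would be d(1 + r + r²) − rd = d(1 + r²) and would omit r/(1 + r + r²), at most 1/3. On either reading the baseline follows at least one cycle of wear.

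**The case against.** The strongest reply is that OP1 to OP5 is right for its stated purpose. Table 14 defines it as the effect of one cycle of wear, and a cycle-specific baseline is the natural choice for that. The study is a descriptive feasibility study with qualitative comparisons (Protocol 14.2.4). This stands: the planned change is not wrong, and what is missing is a second comparison.

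Four stronger readings are tempting, and the documents do not support them.

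- A reader might infer that the markers are never compared with a no-device value. BP2 to OP3 does this in the second and third Ovaprene cycles.
- A reader might infer that a shift arising in Cycle 3 would be hidden. OS1 to OS5 would show it, observed values are summarised at each visit, and all data are listed.
- A reader might infer a large cumulative shift that passes Nugent 7. That would need assumed within-cycle shifts and substantial carry-over, and a score of 7 or more is an entry exclusion here, not a limit during wear.
- A reader might take about 45 enrolled and about 25 completing as the loss between OS1 and OP5B. Those figures run from the end of the baseline cycle and include losses in the Caya cycle. Attrition after OS1 is not given.

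By-visit summaries do not close the gap, because the women contributing at OS1 and at OP5 need not be the same. Symptomatic bacterial vaginosis is itself listed as a possible reason for discontinuation (Protocol 7.5), so those missing at OP5 may be those whose flora changed.

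It is also fair to say that OS1 is not strictly device-naive, since it follows a brief Ovaprene fit test at BP3 and the Caya cycle with nonoxynol-9. It is better called a value before first wear.

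**Conclusion.** The point holds for Nugent score in both PCT cycles and for antibacterial activity and soluble markers at OP5. For these, no planned paired change is measured from a value before first wear, so the planned output cannot report cumulative change in the same women. It does not hold for the markers at OP3.

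The part left out of OP1 to OP5 is whatever carries over from earlier cycles. The illustrative range at OP5B is 0% to 67% of the cumulative shift. It rests on an equal shift in each cycle and a constant carry-over fraction, and neither is in the documents. With no carry-over nothing is lost, but the planned changes alone do not show which case applies.

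The gap is in the planned analysis. Under the protocol's visit text, the samples are already collected.

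**What to change.** Keep OP1 to OP5 as the within-cycle change. Add the following to Protocol Table 14 and SAP 3.7.6, with A and B cycles shown separately:

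- **Nugent score:** paired change from OS1 to OP1A and OP1B, which are at the same cycle phase and show carry-over, and from OS1 to OP5A and OP5B, which shows cumulative change.
- **Antibacterial activity and soluble markers:** the same pairs, only where a pre-insertion OS1 sample exists (non-EVMS sites). At EVMS the OS1 markers are taken 6 hours after insertion, so show any BP1-based change separately. Do not pool it with the other sites: BP1 is midcycle and OS1 is just after menses, so pooling would mix cycle phase with site.
- **Wording:** describe OS1 as before first wear, and note that OS1 to OP5 reflects wear plus intercourse in the PCT cycles.
- **Schedule:** state whether OP1 to OP5 is within A and within B, and reconcile the SAP schedule with Protocol 9.5.1 on when Nugent score is taken.

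The cost is SAP text and a few table columns. There will be fewer paired women at OP5B, so show the number of pairs with each change. The change from OS1 may also look less favourable than the within-cycle change.
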